# The HOPES Trial Version 5 02/23/2018

In the non-predictive scenarios, 6-month GOSE and 4-week DRS scores are independent, while in the predictive scenarios the relationship between 6-month GOSE and 4-week DRS is equal to the observed relationship in the historical data above.

Table 5. The values of the parameters in each of the eight simulated scenarios

	pDc	pDt	pGc0	pGc1	pGt0	pGt1	Pr(GOSE	Pr(GOSE
							good in	good in
							ctrl)	trmt)
Null Pred.	0.40	0.40	0.045	0.800	0.045	0.800	0.347	0.347
Null Non.	0.50	0.50	0.347	0.347	0.347	0.347	0.347	0.347
Low Pred.	0.40	0.60	0.045	0.800	0.045	0.800	0.347	0.498
Low Non.	0.50	0.50	0.347	0.347	0.498	0.498	0.347	0.498
Med Pred.	0.40	0.65	0.045	0.800	0.045	0.800	0.347	0.536
Med Non.	0.50	0.50	0.347	0.347	0.536	0.536	0.347	0.536
Alt Pred.	0.40	0.74	0.045	0.800	0.045	0.800	0.347	0.604
Alt None.	0.50	0.50	0.347	0.347	0.604	0.604	0.347	0.604

The table below provides the operating characteristics (probabilities of success or futility at each possible sample size). As noted above, the trial is powered for effect sizes closer to the "alternative" scenarios, where the trial has over 90% power and a high likelihood of stopping (typically for success) at or before the N=120 interim analysis. Similarly, type I error is controlled at 0.025 for the null scenarios and they are quite likely to stop (typically for futility) at or before the N=120 interim analysis. Power is as expected reduced for effect sizes below where the trial is powered, although the medium scenarios still retain power in the 75-80% range.

Operating characteristics for each of the eight scenarios is summarized in Table 6. The first column provides the scenario name, while the next 6 columns (N=60 through N=350) provides the probability of futility (top number in each cell) and success (bottom number in each cell) at those sample sizes. Thus, for example, in the low predictive scenario the probability of stopping at N=120 and having a successful trial is 0.179. The expected sample size for each trial is given in the E[N] column while the probability of trial success (the sum of the bottom numbers in the N=60 through N=350 cells) is given in the Pr(success) column. The trial is powered for the alternative (bottom two) scenarios, where power is over 90%, although the trial retains modest (75-80%) power for more moderate effect sizes. In the null and alternative scenarios the trial is quite likely to stop at or before the N=120 interim analysis. Results in this table were computed by simulating 10,000 trials in each scenario.

Table 6. Operating Characteristics

	 		1					1
	N=60	N=120	N=180	N=240	N=300	N=350	E[N]	Pr(success)
Null Pred	0.344	0.513	0.024	0.039	0.030	0.026	118.3	0.024
	0.003	0.009	0.004	0.002	0.002	0.004		
Null Non	0.322	0.527	0.026	0.042	0.033	0.030	121.9	0.021
	0.002	0.006	0.003	0.003	0.001	0.005		
Low Pred	0.061	0.227	0.006	0.012	0.016	0.040	180.0	0.637
	0.057	0.179	0.136	0.114	0.075	0.078		
Low Non	0.083	0.248	0.007	0.013	0.013	0.042	182.8	0.594
	0.030	0.160	0.125	0.112	0.077	0.091		
Med Pred	0.035	0.137	0.003	0.005	0.006	0.016	166.9	0.798
	0.088	0.289	0.179	0.130	0.068	0.044		
Med Non	0.053	0.165	0.004	0.005	0.005	0.014	173.3	0.756
	0.050	0.254	0.178	0.138	0.078	0.059		
Alt Pred	0.014	0.042	0.001	0.000	0.000	0.001	134.3	0.942
	0.200	0.438	0.195	0.083	0.019	0.007		
Alt Non	0.024	0.058	0.000	0.000	0.000	0.001	143.2	0.917
	0.115	0.452	0.220	0.096	0.025	0.009		

#### 9.5.3 Interim Analysis on Safety.

The probability of selected adverse events of interest (defined in Section 7), and separately of deaths, will be monitored based on a beta-binomial model. Enrollment will be placed on hold pending DSMB review if the proportion of selected adverse events of interest in the treatment arm is too high in comparison to the control arm or if the proportion of deaths in the treatment arm is too high in comparison to the control arm. The selected adverse events of interest will also include patient deaths.

The DSMB will perform a more detailed review of the selected AEs of interest to determine if the study should continue. In particular, enrollment will be placed on hold if,  $Pr(p1 > p0 \mid data) > 0.98 \text{ OR } Pr(pdeath1 > pdeath0 \mid data) > 0.98$ ,

where p1 and p0 are the proportion of patients with selected AEs of interest in the hypothermia and control arms, respectively, and pdeath1 and pdeath0 are the proportion of patients that died. The prior distributions for p1, p0, pdeath1, and pdeath0 are independent, ran-informative Beta (1, 1). The 0.98 thresholds were selected to adjust partially account for the multiple interim analyses scheduled to occur. We will start to perform the interim analysis on safety for the first 10 patients in each arm randomized, and then other interim analyses will be carried out every 10 patients in both arms (20 patients). The operating characteristics for the stopping rules under various scenarios are summarized in Table 5, with results based on 10000 simulations.

Table 7. summarized the simulation results with interim analyses for safety every 20 patients randomized, assuming there will be 120 patients (60 per arm).

Table 7

Scenario	Selected AEs of	Death		
	Interest	Interest proportions		
	proportions		% trials with at least one	Mean number
	(Control, Treatment)	(Control, Treatment)	hold for safety evaluation	of pts
1	(0.25, 0.10)	(0.125), 0)	0.08%	120
2	(0.25, 0.15)	(0.125, 0.025)	0.4%	120
3	(0.25, 0.25)	(0.125, 0.125)	7.5%	115
4	(0.20, 0.30)	(0.10, 0.20)	39.7%	96
5	(0.20, 0.40)	(0.10, 0.30)	81.1%	66
6	(0.20, 0.50)	(0.10, 0.40)	97.4%	45
7	(0.20, 0.60)	(0.10, 0.50)	99.8%	33

For a trial with 120 patients, there would be five interims (after 20, 40, 60, 80, and 100 patients). We summarized in Table 8 the number of times per simulated trial that enrollment was held. For example, in scenario 7, over half of the simulated trials met the "hold" criterion at every single interim assuming that at each hold the DSMB recommended the trial continue.

**Table 8**. Number of holds per trial in the safety simulation study.

Scenario	Important AE proportions	ons of trials with 0, 1, 2, 3, 4, or 5 holds per trial							
	(Control, Hypothermia)	0	1	2	3	4	5		
1	(0.25, 0.10)	99.9	0.1	0	0	0	0		
2	(0.25, 0.15)	99.6	0.4	0.1	0	0	0		
3	(0.25, 0.25)	92.5	3.9	2.0	1.1	0.4	0.2		
4	(0.20, 0.30)	60.3	13.7	10.1	8.1	5.5	2.4		
5	(0.20, 0.40)	18.9	13.3	16.4	18.9	19.8	12.6		
6	(0.20, 0.50)	2.6	4.8	9.4	19.8	33.5	30.0		
7	(0.20, 0.60)	0.2	0.7	2.7	11.0	33.0	52.4		

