As recommended by the 2007 NINDS TBI workshop, our proposed study would be the first TBI trial to use a specific pathoanatomic injury as opposed to the Glasgow Coma Scale (GCS) as the principal inclusion criterion. Additionally, it would be the first trial to study the efficacy and safety of hypothermia induction using intravascular cooling catheters. In previous trials, hypothermia was induced via surface cooling, a technique that is associated with both significant temperature variability as well as challenges for temperature control in TBI patients requiring emergent neurosurgical operations. Demonstration of safety and efficacy of hypothermia induction with intravascular cooling catheters would increase the generalizability of hypothermia as an intervention. Finally, our study could both confirm the NABIS:H I and NABIS:H II data regarding the benefit of hypothermia for TBI patients who undergo surgical evacuation of intracranial hematomas and potentially provide a mechanism to explain this phenomenon.

Significant morbidity and mortality occurs in traumatic SDH. Mortality rate estimates range from 40-70% of surgical SDH patients(27;28). SDH patients may experience elevated intracranial pressure (ICP), seizures, coagulopathy and hypotension(29-33). SDH patients enrolled in this study are expected to require mechanical ventilation and monitoring of intracranial pressure as part of their routine care(28). Risks associated with hypothermia may include shivering, hypovolemia, electrolyte disorders, hyperglycemia, pneumonia, (small risk of skin lesions if water-circulating surface cooling pads are used), and some risk of catheter-related thrombosis

or possible catheter-related infection with intravascular cooling devices. Risks are minimized by reaching the goal temperature as quickly as possible, rewarming slowly and removing the intravascular catheter within 5 days of placement(33).

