#### 7. **MANAGEMENT OF ADVERSE EXPERIENCES**

Adverse events will be graded according to the USDHHS Common Terminology Criteria for Adverse Events V4.0 (USDHHS, Table 2) and summarized according to body system. Primary focus for analysis will be on 6-month mortality rate, incidence of pneumonia, incidence of DVT/PE, incidence of bleeding and incidence of arrhythmia. For the purpose of safety monitoring, adverse events in the table below of Grade 3 or higher will be classified as "Important AEs" or selected AEs of interest.

Table 2. Selected AEs	Table 2. Selected AEs from USDHHS Common Terminology Criteria for Adverse Events V4.0 USDHHS									
Adverse Event	Grade 1	Grade 2	Grade 3	Grade 4	Grade 5					
Sinus Bradycardia	Asymptomatic, intervention not indicated	Symptomatic, medical intervention indicated	Severe, medically significant, medical intervention indicated	Life-threatening consequences; urgent intervention indicated	Death					
Supraventricular tachycardia	Asymptomatic, intervention not indicated	Non-urgent medical intervention indicated	Medical intervention indicated	Life-threatening consequences; hemodynamic compromise; urgent intervention indicated	Death					
Ventricular arrhythmia	Asymptomatic, intervention not indicated	Non-urgent medical intervention indicated	Medical intervention indicated	Life-threatening consequences; hemodynamic compromise; urgent intervention indicated	Death					
Thromboembolic event	Venous thrombosis (e.g., superficial thrombosis)	Venous thrombosis (e.g., uncomplicated deep vein thrombosis),	Thrombosis (e.g., uncomplicated pulmonary embolism [venous],	Life-threatening (e.g., pulmonary embolism, cerebrovascular event, arterial	Death					

			1	02/23/	2018                                    
		medical intervention indicated	nonembolic cardiac mural [arterial] thrombus), medical intervention indicated	insufficiency); hemodynamic or neurologic instability; urgent intervention indicated	
Pneumonia			Dyspnea and pneumonia symptoms (e.g., aspiration pneumonia); hospitalization indicated; unable to aliment orally	Life-threatening respiratory or hemodynamic compromise; intubation or urgent intervention indicated	Death

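### No safety hold limb in Section 9.5.3 tracks the Section 7 complications apart from death, so the formal trigger is weak against non-fatal harm when mortality is substantial

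*Combined protocol and SAP*

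**What the plan says.** Section 7 picks out by grade the events to be monitored, which it calls important or selected: "adverse events in the table below of Grade 3 or higher will be classified as" such. Table 2 gives death as Grade 5 of each listed event and also has a Death row of its own. The same section sets the safety priorities: "Primary focus for analysis will be on 6-month mortality rate, incidence of pneumonia, incidence of DVT/PE, incidence of bleeding and incidence of arrhythmia".

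Section 9.5.3 says that the probability of selected AEs "and separately of deaths, will be monitored based on a beta-binomial model". Enrolment is held if the posterior probability of a higher rate on hypothermia exceeds 0.98 for either pair of proportions, p1 against p0 for selected AEs or the matching pair for deaths. The unit is the patient: "where p1 and p0 are the proportion of patients with selected AEs of interest in the hypothermia and control arms". It also states: "The selected adverse events of interest will also include patient deaths". All four priors are Beta(1,1). Looks come every 20 patients, and a hold leads to DSMB review. Tables 7 and 8 give the rule's operating characteristics for 120 patients, with control mortality of 10% or 12.5%.

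On expected mortality, Section 2.2 says: "Mortality rate estimates range from 40-70% of surgical SDH patients(27;28").

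**The concern.** The AE limb is in effect death from any cause or a Grade 3+ selected event, counted once per patient. A patient who dies counts the same with or without a complication. If many patients die of the injury, an excess of complications moves this proportion little. If hypothermia lowers mortality, which is what the trial hopes for, fewer deaths offset more complications within the same proportion. Excess deaths are already covered by the second limb. At stake is the only numerical trigger that could respond to the complications that Section 7 names.

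**Working it through.** **1. Reproducing Table 7.** Inputs from Section 9.5.3: Beta(1,1) priors, threshold 0.98, looks at 10, 20, 30, 40 and 50 per arm, hold if either limb fires. With x events in n patients, each posterior is Beta(1+x, 1+n−x). Deaths are nested inside the selected AEs.

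| Scenario | Table 7 holds | Re-run holds | Table 7 mean N | Re-run mean N |
|---|---|---|---|---|
| 1 | 0.08% | 0.10% | 120 | 119.9 |
| 2 | 0.4% | 0.54% | 120 | 119.5 |
| 3 | 7.5% | 7.75% | 115 | 114.9 |
| 4 | 39.7% | 40.2% | 96 | 96.0 |
| 5 | 81.1% | 80.5% | 66 | 66.7 |
| 6 | 97.4% | 97.3% | 45 | 44.5 |
| 7 | 99.8% | 99.9% | 33 | 32.5 |

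A version with AEs independent of deaths and deaths left out of the AE limb does not fit (scenario 4: 49.8%; scenario 5: 90.9%). The nested reading is therefore the one the plan simulated.

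**2. What Table 7 tests.** Subtracting the death rate from the AE rate leaves patients with a selected AE who do not die (control v hypothermia):

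- Scenario 1: 0.25 − 0.125 = 0.125 v 0.10 − 0 = 0.10.
- Scenario 2: 0.125 v 0.15 − 0.025 = 0.125.
- Scenario 3: 0.125 v 0.125.
- Scenarios 4-7: 0.20 − 0.10 = 0.10 v 0.10 (for example 0.30 − 0.20).

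No row has more of these patients on hypothermia. A limb on them alone fires in only 3.2-3.3% of trials in scenarios 4-7, so the detection shown there comes from deaths.

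**3. How the composite dilutes an AE excess.** Let d be mortality, a the AE rate in survivors, and c the AE capture in patients who die relative to survivors (c = 1 means AE and death are independent).

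- Composite: p = d + (1 − d)a. It does not depend on c.
- AEs without the stand-alone Death row: pAE = (1 − d)a + d·c·a.

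Case A, mortality 50% in both arms, AEs 30 v 50%: composite 0.50 + 0.50×0.30 = 0.65 v 0.50 + 0.50×0.50 = 0.75. The 20-point excess becomes 10.

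Case B, mortality 50 v 40%, same AEs: 0.65 v 0.40 + 0.60×0.50 = 0.70. The excess becomes 5 points.

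Case C, mortality 55 v 40%, AEs 20 v 40%: 0.55 + 0.45×0.20 = 0.64 v 0.40 + 0.60×0.40 = 0.64. The excess cancels exactly.

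**4. Trials with at least one hold.** Ranges are c = 100/50/0%.

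| Case | Current rule | Deaths removed from AE limb | Third limb added |
|---|---|---|---|
| A | 26% | 60/47/34% | 63/53/44% |
| B | 13% | 59/53/50% | 60/56/53% |

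In case C the current rule holds about 6%. Removing deaths from the AE limb gives 57-64%.

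The loss is not confined to the cited mortality range. At 20% mortality in both arms and AEs 30 v 50%, the current rule holds 42%, against 50-60% with deaths removed.

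**5. Costs.**

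- No arm difference (50% mortality, AEs 30% in both arms): about 9% now, 12-13% with the third limb.
- Mortality 50 v 40%, equal AE rates: about 2% now, 7-11% with the third limb.
- Mortality 70 v 50%, equal AE rates: 0.5% now, 6-17% with the third limb.
- Deaths 40 v 50% and AEs 30 v 40%, both worse on hypothermia: 37% now. Removing deaths gives 29-35% when capture is incomplete. A third limb joined by OR cannot lower detection.

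**The case against.** Five arguments favour the plan.

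- **Death is a competing event.** Patients who die early cannot go on to have pneumonia or thrombosis, so a composite protects a life-saving arm from looking worse. It also adds detection when deaths and AEs both rise. This stands, and is why the composite should be kept.
- **Complications remain visible.** A reader might infer that excess complications would go unseen. The documents do not support that. Section 9.4 has safety monitoring every 20 patients, Section 9.5 reports AEs by type, frequency and severity, and Section 10.4 sends SAEs to the medical monitor and then the DSMB. The research monitor can stop the protocol.
- **The 40-70% mortality is not this trial's rate.** It describes surgical cases generally. Section 11.4 uses up to 70% for death or severe disability together. Section 9.5.2 assumes 0.347 good outcome in controls, so at most 1 − 0.347 = 65.3% could die. Eligibility is restricted, and interim looks include short follow-up. This stands as a limit on size. At 25% equal mortality with AEs 30 v 50%, the contrast narrows to 39% now against 48-60% with deaths removed.
- **Sizes rest on assumed AE rates.** This also stands. With AEs 30 v 40% at 50% mortality, removing deaths moves holds only from 14% to 28/23/19%.
- **Counting death is deliberate.** Table 2 and the Table 7 simulation are consistent with it. That shows intent, but not that the rule can detect non-fatal harm.

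**Conclusion.** The point holds for the formal trigger and should be corrected. Section 9.5.3 has no numerical limb for the Section 7 complications apart from death, and Table 7 contains no scenario of excess non-fatal harm on hypothermia. With substantial mortality the trigger is much less sensitive to such harm: about 26% of trials held in case A and 13% in case B.

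A reader might go further and conclude that a mortality benefit always cancels an AE excess. It does not. Cancellation is complete only for some combinations, such as case C, and is otherwise partial: at 40 v 30% mortality with AEs 20 v 40%, the AE limb still fires in 13.5% of trials. Nor does it follow that deaths should simply be taken out, since that can lose detection when both outcomes worsen.

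The non-fatal AE rates, their independence from death, the capture in patients who die and the mortality differences are all assumptions; the documents give none of them for non-fatal harm. The direction is clear from the algebra: at equal mortality the composite shrinks an AE excess by the factor 1 − d.

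**What to change.** In Section 9.5.3 keep the composite and death limbs and add a third hold condition: Pr(pAE1 > pAE0 | data) > 0.98. Define pAE as the proportion of patients with at least one Grade 3 or higher Table 2 event other than the stand-alone Death row. Count it in all randomised patients, including those who later die. A Table 2 event that is itself fatal counts.

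Re-run Tables 7 and 8 with this limb. Add rows with more non-fatal harm on hypothermia and rows with mortality in the cited range, and state the AE capture assumed in patients who die.

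The work is a short addition to 9.5.3 and a re-run of an existing simulation. The price is the extra holds in step 5 of the working, each a pause for DSMB review and not a termination. The DSMB should be told that a survival benefit alone can trigger the new limb, because more survivors remain at risk of an AE. Removing deaths from the existing AE limb is the weaker alternative.

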#### DATA COLLECTION, SITE MONITORING, AND ADVERSE EVENT REPORTING

#### 10.1 Records to Be Kept

Data collection will be based off Case Report Forms (CRFs) derived directly from the NIH TBI Common Data Elements project (www.commondataelements.ninds.nih.gov/TBI.aspx). This trial will leverage the CRFs and web-based database already developed by REDCap (Research Electronic Data Capture - Vanderbilt University) to utilize the TBI Common Data Elements project in which the University of Pittsburgh ([name], site PI) participated. The CRFs have already been designed and implemented, which will contribute significantly to rapid, smooth rollout of the trial proposed herein.

Study personnel will collect information on subject characteristics such as demographics, medical history, and injury information. The initial assessment of the subject will be recorded including physical and neurological examination, vital signs, laboratory tests, and radiographic

imaging. In addition, as part of the baseline data collection, family members will be asked to complete a contact information form with the names, addresses and phone numbers of other people who could assist in locating him/her if the study coordination cannot locate him/her for the scheduled phone interviews. The study will consider the use of a locator service for patients potentially lost to follow-up.

Additional CRFs will be generated to record disease and injury-related events, treatments and interventions during the initial hospitalization, and safety data for adverse event reporting. The outcome end points will be based off the Core measures of the TBI Common Data Elements.

Federal law now holds the statute of limitations at six years to bring forward an allegation of research misconduct. In response to this extension, research records must be retained for a sufficient period to investigate an allegation of research misconduct - - a minimum period of six years. Additionally, existing Federal regulations [56 CFR 56.115(b)] require that IRB records be retained for at least 3 years after completion of the research. All records must be accessible for inspection and copying by authorized representatives of HHS and Food and Drug Administration at reasonable times and in a reasonable manner. At the end of the three year period, the IRB records may be boxed, labeled and sent to central storage for an additional 3-10 years. A log of stored records is maintained in the IRB office for retrieval if files are needed for audit or other purposes.

Records will be maintained in a de-identified manner in a secure, locked location to ensure confidentiality. Subjects will not be identified in any manner in any publications resulting from this project.

# **10.2 Role of Data Management**

De-identified data will be collected from the pre-hospital period through 6 months post injury. A linking list will be maintained by the investigative team at each site to allow for patient follow-up. Protected health information (PHI) is confidential and not shared outside the study team. Written data will be stored in locked areas; electronic data will be password protected in secure zones. Patient name and contact information will be separated from subject data. The PI will monitor protocol compliance and data integrity. Routine data audits will be conducted internally to assure consistency and integrity of the data. Additionally, an independent data auditor will verify data quality.

10.2.1 Data Management Overview. The statistical center will manage the study specific database. Data will be linked by unique ID. The study statistician will independently review the forms and the entered data. The database will incorporate quality control checks at data entry, and quality assurance programs will be written for acquisition, management, tracking and retrieval and will be run regularly. The database will be backed up onto separate media. The database is maintained for statistical analysis purpose only; thus, all electronic files will be de- identified. The database will be password protected and maintained in secure research offices in a secure research building. Data validation checks identifying outliers will generate queries which will be evaluated and if necessary returned to the clinical study site for data validation. An audit trail will be maintained on changes to the database.

#### 10.3 Quality Assurance

The Medical Monitor will oversee the Quality Assurance procedures related to the ICU management of episodes of intracranial hypertension. [name] will ensure all outcomes personnel are properly trained and will review scoring of all outcome measures.

Database queries will be designed and implemented to oversee compliance with all study documentation and timely completion of CRFs. Protocol deviations, record completion, and regulatory compliance will be reviewed by PIs and Site Study Coordinators at each monthly conference call. All study documents and pertinent records will be available for inspection by the DSMB, the sponsor, or other designated monitoring authority.

